## List of abbreviations

AE	Adverse Event
AERP	Atrial effective refractory period
AF	Atrial fibrillation
ALP	Alkaline Phosphatase
ALT	Alanine Aminotransferase
ANCOVA	Analysis of covariance
AST	Aspartate Aminotransferase
ATC	Anatomical Therapeutic Chemical
AUC	Area under the curve
AV	Atrioventricular
BMI	Body Mass Index
BUN	Blood Urea Nitrogen
CK	Creatine Kinase
C max	Maximum concentration
CMO&PS	Chief Medical Office and Patient Safety
CNS	Central nervous system
CRF	Case Report/Record Form (paper or electronic)
CRO	Contract Research Organization
CSR	Clinical study report
DBP	Diastolic Blood Pressure
EC 90	90% Effective concentration
ECG	Electrocardiogram
EDC	Electronic Data Capture
EMA	European Medicines Agency
EOS	End of Study
FIH	First-in-human
FSH	Follicle Stimulating Hormone
GCP	Good Clinical Practice
GCS	Global Clinical Supply
GGT	Gamma-glutamyl transferase
GLDH	Glutamate Dehydrogenase
GLP	Good Laboratory Practices
h	Hour
HBcAg	Hepatitis B core antigen
HBsAg	Hepatitis B virus surface antigen
HCV	Hepatitis C Virus
HF	Heart failure
HIV	Human immunodeficiency virus
i.v.	Intravenous
IB	Investigator's Brochure
ICF	Informed Consent Form

ICH	International Council for Harmonization of Technical Requirements for Pharmaceuticals for Human Use
IEC	Independent Ethics Committee
IN	Investigator Notification
INR	International Normalized Ratio
IRB	Institutional Review Board
IUD	Intrauterine device
IUS	Intrauterine system
LDH	lactate dehydrogenase
LFT	Liver function test
LLOQ	lower limit of quantification
MedDRA	Medical dictionary for regulatory activities
mg	milligram(s)
mL	milliliter(s)
NIRT	Novartis Interactive Response Technology
NOAC	Novel oral anticoagulant
P-gp	P-glycoprotein
PACU	Post-anesthesia care unit
PCR	Protein-creatinine ratio
PD	Pharmacodynamic(s)
PK	Pharmacokinetic(s)
PoC	Proof of Concept
PT	prothrombin time
QMS	Quality Management System
QTcF	QT interval corrected by Fridericia's formula
SA	Sinoatrial
SAE	Serious Adverse Event
SAP	Statistical Analysis Plan
SBP	Systolic Blood Pressure
sCR	serum creatinine
SD	standard deviation
SGOT	Serum Glutamic Oxaloacetic Transaminase
SGPT	Serum Glutamic Pyruvic Transaminase
SMQ	Standardized MedDRA Query
SUSAR	Suspected Unexpected Serious Adverse Reaction
TdP	Torsades de Pointes
TIA	Transient ischemic attack
ULN	upper limit of normal
UTI	Urinary Tract Infection
WHO	World Health Organization
WPW	Wolff-Parkinson-White

## Glossary of terms

Additional treatment	Medicinal products that may be used during the clinical trial as described in the protocol, but not as an investigational medicinal product (e.g. any background therapy)
Assessment	A procedure used to generate data required by the study
Biologic Samples	A biological specimen including, for example, blood (plasma, serum), saliva, tissue, urine, stool, etc. taken from a study participant
Coded data	Personal Data which has been de-identified by the investigative center team by replacing personal identifiers with a code.
Cohort	A specific group of participants fulfilling certain criteria and generally treated at the same time
Control drug	A study drug (active or placebo) used as a comparator to reduce assessment bias, preserve blinding of investigational drug, assess internal study validity, and/or evaluate comparative effects of the investigational drug
Discontinuation from study treatment	Point/time when the participant permanently stops receiving the study treatment for any reason (prior to the planned completion of study drug administration, if any). Participant agrees to the other protocol required assessments including follow-up. No specific request is made to stop the use of their samples or data.
Dosage	Dose of the study treatment given to the participant in a time unit (e.g., 100 mg once a day, 75 mg twice a day)
Electronic Data Capture (EDC)	Electronic data capture (EDC) is the electronic acquisition of clinical study data using data collection systems, such as Web-based applications, interactive voice response systems and clinical laboratory interfaces. EDC includes the use of Electronic Case Report Forms (eCRFs) which are used to capture data transcribed from source data/documents used at the point of care
End of the clinical trial	The end of the clinical trial is defined as the last visit of the last participant.
Enrollment	Point/time of participant entry into the study at which informed consent must be obtained. The action of enrolling one or more participants.
Healthy volunteer	A person with no known significant health problems who volunteers to be a study participant
Intercurrent events	Events occurring after treatment initiation that affect either the interpretation or the existence of the measurements associated with the clinical question of interest.
Investigational drug/ treatment	The drug whose properties are being tested in the study
Medication number	A unique identifier on the label of medication kits
Mis-randomized participants	Mis-randomized participants are those who were not qualified for randomization and who did not take study treatment, but have been inadvertently randomized into the study
Other treatment	Treatment that may be needed/allowed during the conduct of the study (i.e. concomitant or rescue therapy)
Participant	A trial participant (can be a healthy volunteer or a patient). "Participant" terminology is used in the protocol whereas term "Subject" is used in data collection.

Participant number	A unique number assigned to each participant upon signing the informed consent. This number is the definitive, unique identifier for the participant and should be used to identify the participant throughout the study for all data collected, sample labels, etc.
Period	The subdivisions of the trial design (e.g. Screening, Treatment, Follow-up) which are described in the Protocol. Periods define the study phases and will be used in clinical trial database setup and eventually in analysis
Personal data	Participant information collected by the Investigator that is coded and transferred to Novartis for the purpose of the clinical trial. This data includes participant identifier information, study information and biological samples.
Premature participant withdrawal	Point/time when the participant exits from the study prior to the planned completion of all study drug administration and/or assessments; at this time all study drug administration is discontinued and no further assessments are planned
Randomization	The process of assigning trial participants to investigational drug or control/comparator drug using an element of chance to determine the assignments in order to reduce bias.
Randomization number	A unique identifier assigned to each randomized participant
Re-screening	If a participant fails the initial screening and is considered as a Screen Failure, he/she can be invited once for a new Screening visit after medical judgment and as specified by the protocol.
Screen Failure	A participant who did not meet one or more criteria that were required for participation in the study
Source Data/Document	Source data refers to the initial record, document, or primary location from where data comes. The data source can be a database, a dataset, a spreadsheet or even hard-coded data, such as paper or eSource
Start of the clinical trial	The start of the clinical trial is defined as the signature of the informed consent by the first participant
Study treatment	Any drug or combination of drugs or intervention administered to the study participants as part of the required study procedures; includes investigational drug(s), control(s) or background therapy
Study treatment discontinuation	When the participant permanently stops taking any of the study drug(s) prior to the defined study treatment completion date (if any) for any reason; may or may not also be the point/time of study discontinuation
Treatment arm/group	A treatment arm/group defines the dose and regimen or the combination, and may consist of 1 or more cohorts.
Variable (or endpoint)	The variable (or endpoint) to be obtained for each participant that is required to address the clinical question. The specification of the variable might include whether the participant experiences an intercurrent event.

Commercially Confidential Information

Commercially Confidential Information

Commercially Confidential Information

Commercially Confidential Information

Commercially Confidential Information

---

Commercially Confidential Information

---

Commercially Confidential Information

---

Commercially Confidential Information

Commercially Confidential Information

---

Commercially Confidential Information

Commercially Confidential Information

Commercially Confidential Information

## Protocol summary

Protocol number	CHSY244X2201
Full Title	A randomized, placebo-controlled, investigator- and participant-blinded study to evaluate the efficacy, safety, tolerability, and pharmacokinetics of HSY244 in participants with atrial fibrillation
Brief title	A study to evaluate the efficacy, safety, tolerability, and pharmacokinetics of HSY244 in participants with atrial fibrillation
Sponsor and Clinical Phase	Novartis Institutes for BioMedical Research Phase II
Investigation type	Drug
Study type	Interventional
Purpose and rationale	The purpose of this study is to evaluate the efficacy, safety, tolerability, and pharmacokinetics of HSY244 in participants with atrial fibrillation (AF). HSY244 is a potent inhibitor of GIRK1/4 channels, which are believed to play an important role in AF. GIRK1/4 inhibition is expected to restore sinus rhythm without undesirable effects on ventricular repolarization and hence, may offer superior properties for pharmacologic cardioversion of AF. HSY244 is planned to be developed as an intravenous (i.v.) infusion for the acute cardioversion of AF to sinus rhythm.
Primary Objective(s)	The primary objective of this study is to evaluate the efficacy of HSY244 to restore sinus rhythm in participants with AF.
Secondary Objectives	To evaluate the safety and tolerability of HSY244 in participants with AF To evaluate the pharmacokinetics of HSY244 in participants with AF
Study design	
This is a randomized, placebo-controlled, investigator- and participant-blinded study to evaluate the efficacy, safety, tolerability, and pharmacokinetics of HSY244 in participants with AF. An initial cohort (Cohort 1) of approximately 29 participants (approximately 20 participants receiving HSY244) is planned to be enrolled to evaluate a single 150 mg i.v. dose of HSY244 for AF cardioversion to sinus rhythm.
 
Commercially Confidential Information
 
Participants with AF that meet clinical criteria for direct current cardioversion will be screened, and on Day 1, after eligibility is confirmed, administration of a 15 minute i.v. infusion of HSY244 or placebo will occur. Participants will then be monitored for cardioversion to sinus rhythm. For those remaining in AF after 90 minutes, direct current cardioversion can be performed. Participants will be monitored for at least 3 hours, although overnight observation will be available. Participants will be evaluated for safety and pharmacokinetic assessments during end of study assessments, which are to occur on Day 5 (96 hours post dose) ± 24 hours. An interim analysis in Cohort 1 is planned after approximately 10 participants have received HSY244 and completed end of study assessments.
 
Commercially Confidential Information

Study population	
The study population will include hemodynamically stable men and women between 18 and 80 years of age with a clinical indication for direct current cardioversion of AF, with the current AF episode lasting between 6 hours and 60 days.
 
In Cohort 1, a total of approximately 20 participants will receive HSY244 and a total of approximately 29 participants with AF will be randomized. The randomization ratio will be a 5:1 ratio of HSY244 and placebo.
 
Commercially Confidential Information

Key Inclusion criteria	
 
• Hemodynamically stable men and women between 18 and 80 years of age with a clinical indication for direct current cardioversion of AF
 
• Current episode of AF has been ongoing for ≥6 hours and ≤60 days
 
• Successful initiation and achievement of therapeutic levels of national guideline and institution-specific anticoagulation therapy as appropriate for the duration of the AF episode and risk for the participant
 
• Completion of national guideline and institution-specific imaging evaluation for left atrial thrombi as appropriate for the duration of AF episode and risk for the participant
 
• Participants must weigh at least 60 kg to participate in the study, and must have a body mass index (BMI) within the range of 18 - 45 kg/m^2. BMI = Body weight (kg) / [Height (m)]
 
• Written informed consent must be obtained before any assessment is performed and only participants able to provide written informed consent themselves will be included in this study
 

Key Exclusion criteria	
 
• Use of any class I or III anti-arrhythmic medication, or other prohibited medications, within 5 half-lives before randomization, including use of amiodarone within 3 months before randomization
 
• History or current diagnosis of electrocardiogram (ECG) abnormalities or cardiac rhythm disorders indicating significant risk of safety for participant as determined by the Investigator's interpretation of the ECG findings
 
• Attempted or unsuccessful cardioversion within 2 weeks prior to randomization
 
• Presence of known severe mitral regurgitation and/or known severely dilated left atrium
 
• Pre-existing or tachycardia-induced moderate to severe cardiac dysfunction (New York Heart Association class III or IV)
 
• History within the preceding 3 months prior to randomization of either a: myocardial infarction, unstable angina, cardiac surgery, or a percutaneous coronary intervention
 
• History of confirmed stroke or transient ischemic attack (TIA)
 
• History or current diagnosis of any seizure disorder or major neurological disorder or major psychiatric disorder
 
• Sexually active males, including those post-vasectomy, must use a condom during sexual intercourse for at least 96 hours after dosing to prevent delivery of the drug via seminal fluid and should not father a child during this period
 
• Women must be either of non-childbearing potential or child-bearing potential using highly effective non-hormonal contraception
 

Study treatment	HSY244 or placebo
Efficacy assessments	Digital Holter (continuous ECG) monitor

Pharmacokinetic assessments	PK profile as measured by Cmax, Tmax, and AUClast from the plasma concentration-time data
Key safety assessments	Adverse event monitoring, vital signs, physical examinations, monitoring of laboratory markers in blood and urine, ECG parameters
Other assessments	Commercially Confidential Information
Data analysis	The rate of conversion to sinus rhythm for HSY244 and placebo will be compared using Fisher's Exact test. The difference in the conversion rates between HSY244 and placebo will be reported along with the 80% confidence limits for the difference and the p-value from Fisher's Exact test. Results may be reported for the subpopulations of participants with and without heart failure.
Key words	Atrial fibrillation, Arrhythmia, Pharmacological cardioversion, GIRK1/4

## 1 Introduction

### 1.1 Background

Atrial fibrillation (AF) is a common cardiac arrhythmia that increases in prevalence with age. AF affects approximately 2% of people under the age of 65 and about 9% of people above the age of 65. In the US, AF accounts for more than 467,000 hospitalizations and contributes to more than 99,000 deaths a year (January et al 2014). A 2010 health survey estimated that 33 million people worldwide had AF (Chugh et al 2014). With the aging of the population, the prevalence of AF is expected to rise substantially in the future adding burden to healthcare systems. AF is highly prevalent among individuals with heart failure (HF) with an increasing frequency of AF as severity of HF increases (Trulock et al 2014). Patients with AF and HF have worse outcomes as compared to patients with HF alone, regardless of the degree of cardiac dysfunction (Olsson et al 2006).

AF can lead to symptoms such as palpitations, dyspnea, chest pain, and fatigue. AF is associated with an increased risk of stroke, congestive heart failure, and a decreased quality of life. Cardioversion of AF to sinus rhythm remains an important option for patients with AF. The most commonly utilized method of restoring sinus rhythm is direct current cardioversion in which an electric shock is delivered to the heart under sedation or anesthesia. This procedure is generally performed under the supervision of a cardiologist and an anesthesiologist. Pharmacologic cardioversion is another option, but not commonly performed even though it is less invasive and could be initiated more rapidly as it does not require sedation or anesthesia. Antiarrhythmic drugs such as flecainide, propafenone, ibutilide, dofetilide, or amiodarone have demonstrated some efficacy as AF cardioversion agents, but they are limited by poor efficacy, slow onset of action, or undesired effects on ventricular repolarization leading to a prolonged QT interval and risk of torsades de pointes. There is an unmet need for a safe and effective drug that can rapidly cardiovert AF patients to sinus rhythm.

The cardiac acetylcholine-sensitive inwardly rectifying K+ current ( $I_{KACH}$ ), is mediated by a channel with two subunits, GIRK1 and GIRK4, assembled as heterotetramers (Voigt et al 2014). In the heart,  $I_{KACH}$  channels are primarily expressed in the sinoatrial (SA) node, atrioventricular (AV) node, and atrial myocytes.  $I_{KACH}$  is believed to have a physiologic role in the regulation of sinus node automaticity and in the repolarization of atrial myocytes. As GIRK1/4 expression is largely absent in the ventricles, inhibition of GIRK1/4 is believed to represent an attractive antiarrhythmic drug target since such a blocker would be expected to have little to no effects on ventricular repolarization and thus be devoid of pro-arrhythmic ventricular side effects.

Increased activation of  $I_{KACH}$  channels has been proposed to contribute to AF by leading to a shortening of the atrial action potential duration. Activation of  $I_{KACH}$  has been observed in experimental models of AF induced by tachypacing, and constitutive  $I_{KACH}$  activity has been observed in atrial myocytes from patients with chronic AF (Dobrev et al 2005). Mechanistically, by shortening the atrial action potential duration and decreasing the atrial effective refractory period (AERP),  $I_{KACH}$  activity is assumed to increase vulnerability to electrical reentry promoting the propagation of AF. Indeed, several antiarrhythmic drugs such as amiodarone, flecainide, and verapamil have been shown to possess  $I_{KACH}$  blocking effects, and tertiapin, a bee venom peptide that selectively blocks  $I_{KACH}$ , has been shown to terminate AF in both dog and guinea pig models without affecting PR, QRS, and QT intervals (Voigt et al 2014). These

data suggest that a selective pharmacologic inhibitor of GIRK channels has potential as a novel antiarrhythmic drug for the cardioversion of patients with AF.

HSY244 is a potent inhibitor of GIRK channels. Novartis is developing HSY244 as an intravenous (i.v.) infusion for the acute cardioversion of patients with AF.

Commercially Confidential Information

The most relevant data for the present study are summarized in the sections below. For detailed information, please refer to the Investigator's Brochure.

## 1.2 Purpose

The purpose of this study is to evaluate the efficacy, safety, tolerability, and pharmacokinetics of HSY244 in participants with AF, with and without HF. HSY244 is a potent inhibitor of GIRK1/4 channels, which are believed to play an important role in AF.

Commercially Confidential Information

## 2 Objectives and endpoints

**Table 2-1 Objectives and related endpoints**

Objective(s)	Endpoint(s)
Primary objective(s)	Endpoint(s) for primary objective(s)

To evaluate the efficacy of HSY244 to restore sinus rhythm in participants with AF

	

Conversion to sinus rhythm for at least 1 minute within 90 minutes from the start of study drug administration

Secondary objective(s)	Endpoint(s) for secondary objective(s)

To evaluate the safety and tolerability of HSY244 in participants with AF

To evaluate the pharmacokinetics of HSY244 in participants with AF

	

Results of safety assessments including adverse events, vital signs, ECG parameters, and laboratory assessments of blood and urine.

HSY244 plasma AUClast, Cmax, and Tmax after i.v. administration

Exploratory objective(s)	Endpoint(s) for exploratory objective(s)

Commercially Confidential Information

### 3 Study design

This is a randomized, placebo-controlled, investigator- and participant-blinded study to evaluate the efficacy, safety, tolerability, and pharmacokinetics (PK) of HSY244 in participants with AF, with and without HF. An initial cohort (Cohort 1) evaluating a 150 mg i.v. dose of HSY244, administered over a 15-minute infusion, is planned to be enrolled.

Commercially Confidential Information

#### Figure 3-1 Study Design

Commercially Confidential Information

For Cohort 1 CCI the following will occur:

A screening period of up to 3 days (72 hours) will be used to assess eligibility. After eligibility is confirmed, participants will be randomized to either HSY244 or placebo. Prior to study drug administration, pre-dose assessments will be completed (refer to [Section 8](#) for complete details). Standard clinical care practices should be followed per Investigator's discretion, including but not limited to bedside telemetry and application of defibrillator pads. A study 12-lead Holter (continuous ECG) monitor will be applied for continuous heart rate and rhythm monitoring for 24 hours and will also allow for single-timepoint ECG tracings to be captured. After the participant's ongoing AF episode is confirmed, study drug administration of a 15 minute i.v. infusion of HSY244 or placebo will begin; this is time '0' as related to all post-dose assessments. After the start of study drug administration, the participant will be monitored for cardioversion to sinus rhythm. If a participant is still in AF at 90 minutes after the start of study drug administration, direct current cardioversion may be applied at a time deemed appropriate by the investigator. Standard clinical care approaches should be followed for direct current

cardioversion but alternatives should be considered for the medications on the prohibited medication list (Table 6-2) until the EOS visit has occurred.

For the first 120 minutes (2 hours) after study drug administration, the participant should be resting in the supine or semi-recumbent position with minimal disturbances to allow for assessments of heart rate CCI. If direct current cardioversion is applied at 90 minutes, there should be an additional 30 minutes afterward during which the participant should be resting in the supine or semi-recumbent position with minimal disturbances to allow for assessments of heart rate CCI.

The participant should be monitored for at least 180 minutes (3 hours), after study drug administration for safety and blood sampling; this monitoring period can be extended through 24 hours if deemed necessary or appropriate by the Investigator and/or for convenience for the participant. The participant can be transferred to other locations within the study site (i.e., to a post-anesthesia care unit [PACU], hospital ward, or clinical trials unit given site staff is appropriately trained) during the 3 hour monitoring period (or for 24 hours if observation period is extended), at the discretion of the Investigator, as long as the participant can remain undisturbed (i.e., remain in supine/semi-recumbent position for the first 2 hours), and the study protocol requirements, assessments and appropriate standard clinical care practices are possible.

Commercially Confidential Information

If the participant remains on-site overnight, Day 2 (24 hours post-dose) assessments should be completed before the participant's release from the study site. If the participant does not remain at the site overnight, the site will call the participant on Day 2 (24 hours post dose  $\pm$ 4 hours) to check on AEs, as well as to guide the participant for the removal of the Holter device. The participant should remain resting in a supine or semi-recumbent position for at least 15 minutes prior to the removal of the Holter (continuous ECG) monitor to allow for the assessment of resting heart rate CCI. The participant is required to return to the study site within  $\pm$ 24 hours of Day 5 (96 hours post dose) for end of study (EOS) assessments.

A total of approximately 29 participants are planned to be randomized in Cohort 1, of which approximately 20 will receive HSY244. Participants will be randomized in a 5:1 HSY244-to-placebo ratio.

Commercially Confidential Information

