## 4 Rationale

### 4.1 Rationale for study design

**Table 4-1 Rationale for study design**

Study Design Aspect	Rationale
Overall	
This is a randomized, placebo-controlled, investigator- and participant-blinded study to evaluate the efficacy, safety, tolerability, and pharmacokinetics of HSY244 in participants with AF, with or without HF. The study design was chosen to minimize bias. An initial cohort (Cohort 1) evaluating a 150 mg i.v. dose of HSY244 or placebo given over a 15-minute infusion is planned to determine if this dose will restore sinus rhythm to participants with AF.

Commercially Confidential Information
	
Randomization (strata, allocation ratio)	
Randomizing participants 5:1 to receive HSY244 or placebo will maintain the blind and enable detection of possible differences in each group.

Participant and investigator blinding	
Blinding of participants and the investigator allows for an unbiased assessment of study endpoints, particularly for subjective readouts, such as adverse events. Limited unblinding of the Sponsor as detailed in Table 6-3 will improve the accuracy of safety-related decisions.

Duration of study	
The study duration minimizes the burden to the participants and allows the Sponsor to collect the data required for efficacy, safety, tolerability, and PK readouts.

Placebo comparator	
The use of placebo as a comparator is to provide a comparison group for an unbiased collection and assessment of efficacy, safety and tolerability.

Observation period	
This allows for close observation of safety and tolerability during the time of the highest exposure to HSY244. At 180 minutes (3 hours), the time of planned discharge, exposure is predicted to be below the threshold for physiological effect for both Cohort 1

Commercially Confidential Information
	

The observation period can be increased if deemed necessary or appropriate by the Investigator and/or for the convenience for the participant.
	

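### Cohort 1's stated total (about 29), HSY244 number (about 20) and 5:1 ratio do not fit together, so the planned placebo number could be 4, 5 or 9

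*Protocol*

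**What the plan says.** All three figures appear together in two places in the protocol.

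- **Section 3 (Study design)**, in adjacent sentences: "A total of approximately 29 participants are planned to be randomized in Cohort 1, of which approximately 20 will receive HSY244" and "Participants will be randomized in a 5:1 HSY244-to-placebo ratio".
- **Protocol summary.** The study design entry says "An initial cohort (Cohort 1) of approximately 29 participants (approximately 20 participants receiving HSY244) is planned to be enrolled". The study population entry repeats about 20 and about 29, this time as randomised, and adds "The randomization ratio will be a 5:1 ratio of HSY244 and placebo".

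Other sections repeat parts of this. Section 5 and SAP 1.4 give 29 and 20. Table 4-1 gives the ratio ("Randomizing participants 5:1 to receive HSY244 or placebo will maintain the blind and enable detection of possible differences in each group"), and so does Section 6.1.3.

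The unit counted also varies. The summary and SAP 1.4 speak of 29 enrolled, while the summary, Section 3 and Section 5 speak of 29 randomised. The glossary defines enrolment as "Point/time of participant entry into the study at which informed consent must be obtained", which is an earlier point than randomisation.

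No visible passage gives a planned placebo number, an allowance for participants who are randomised but not dosed, or a second ratio. Protocol 12.8.1 (sample size) and the text directly after these figures are redacted.

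**The concern.** A total, one arm's size and an allocation ratio are three statements about two unknowns, so any two fix the third. Here each pair gives a different placebo arm.

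The primary analysis is a Fisher's exact test of conversion on HSY244 against placebo, reported with 80% intervals (Protocol 12.4.2, SAP 6.1.3). In a design this unbalanced, the small control arm limits both the precision of the placebo rate and what the test can show. Going from 4 to 9 controls more than doubles that arm. A reader cannot tell which control group was planned, or which split any stated power rests on.

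**Working it through.** **Inputs** (Protocol summary and Section 3): total N = 29; HSY244 n = 20; ratio 5:1, so 5/6 on HSY244 and 1/6 on placebo.

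**1. Trying to reproduce the stated figures**

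| Figures kept | Calculation | HSY244 : placebo |
|---|---|---|
| 29 and 5:1 | 29 × 5/6 = 24.2; 29/6 = 4.8 | 24 : 5, against a stated 20 on HSY244 |
| 20 and 5:1 | 20/5 = 4; 20 × 6/5 = 24 | 20 : 4, against a stated total of 29 |
| 29 and 20 | 29 − 20 = 9; 20/9 = 2.2 | 20 : 9, against a stated 5:1 |

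**2. Does rounding close the gap?** Allow two participants either way. Then 18 to 22 on HSY244 at 5:1 implies a total of 21.6 to 26.4, whereas 29 ± 2 is 27 to 31. The ranges do not meet.

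**3. Does chance close it?** Under simple random allocation at 5/6, P(20 or fewer of 29 on HSY244) = 0.041. These are planned numbers in any case.

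**4. Readings under which all three could hold.** Each is solved backwards from the figures and needs something that no visible text states.

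- *(a) Randomised but not dosed.* Randomisation comes first ("After eligibility is confirmed, participants will be randomized to either HSY244 or placebo"), and dosing waits for a further check ("After the participant's ongoing AF episode is confirmed, study drug administration of a 15 minute i.v. infusion of HSY244 or placebo will begin"). Getting from 24.17 to 20 on HSY244 needs 1 − 20/24.17 = 17.2% undosed, or 5 of 29. That leaves 4.83 × 0.828 = 4.0 treated on placebo, so about 20:4.
- *(b) Replacements.* 24 plus the Section 5 maximum of 4 is 28, and one undosed participant makes 29: again about 20:4. This requires 29 to include replacements, and receiving HSY244 to mean completing the infusion.
- *(c) More than one ratio.* For example, 25 at 2:1 and 4 at 5:1: 25 × 2/3 + 4 × 5/6 = 20.0 on HSY244 and 25/3 + 4/6 = 9.0 on placebo.

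**5. What the split changes**

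*Precision, with no assumed conversion rates.* With no placebo conversions, the exact (Clopper-Pearson) 80% upper limit is 1 − 0.1^(1/n).

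*Fisher threshold.* The level is not visible. I assume two-sided 0.20, to match the 80% intervals, and no placebo conversions.

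| | 20:4 | 24:5 | 20:9 |
|---|---|---|---|
| 80% upper limit, placebo rate | 44% | 37% | 23% |
| HSY244 conversions needed | 10/20 (p = 0.114) | 9/24 (p = 0.153) | 5/20 (p = 0.153) |

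*Power.* Full enumeration of both binomials, two-sided 0.20. All rates are assumptions.

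| HSY244 vs placebo | 20:4 | 24:5 | 20:9 |
|---|---|---|---|
| 50% vs 5% | 48.9% | 77.0% | 87.6% |
| 60% vs 5% | 75.4% | 90.1% | 96.1% |
| 70% vs 5% | 90.6% | 96.7% | 99.2% |
| 50% vs 10% | 40.3% | 63.5% | 74.9% |
| 60% vs 10% | 64.6% | 80.2% | 89.4% |
| 70% vs 10% | 82.7% | 91.1% | 96.6% |

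The gap from 24:5 to 20:9 is 2.5 to 11.4 points; from 20:4 to 20:9 it is 8.6 to 38.7 points. The order does not depend on the 0.20 level: at two-sided 0.05, 50% vs 10% gives 8.7%, 25.1% and 50.7%.

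**The case against.** The strongest reply is redaction. Blacked-out text follows these figures in the summary and in Sections 3 and 5, and it covers the sample size and interim sections. The full plan may give the placebo number and the reason for 29. That stands: this review cannot say that the plan lacks a placebo number or that a particular figure is wrong. It does not rescue the unredacted sentences, which put all three figures side by side with no qualification.

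Second, 4 and 5 can belong to one plan: 5 randomised to placebo, of whom about 4 are treated. That is right, and it makes the main contrast 4 or 5 against 9. It is also why the fix asks for randomised and treated numbers separately.

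Third, the ratio sentences do not name Cohort 1 themselves. In the summary and Section 3, however, they follow directly on the Cohort 1 counts.

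Fourth, the power figures rest on an assumed level and assumed rates, and 20:4 has five fewer participants than 20:9, so the largest gaps are not a pure effect of the split. With 29 treated either way, the gap is at most about 11 points over the grid, and it is small if the drug effect is large. The upper limits for the placebo rate need neither assumption.

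Fifth, SAP 6.1.3 lets placebo participants be pooled across cohorts, which could enlarge the control group. Pooling is optional, so it does not settle the number planned for Cohort 1.

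**Conclusion.** The concern holds on the visible text. About 29 randomised, about 20 receiving HSY244 and 5:1 cannot all be true as written, and neither rounding nor chance explains the gap. The planned Cohort 1 placebo number could be 4, 5 or 9, depending on which figures are kept and whether randomised or treated participants are meant.

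The effect on the primary comparison can be material. The 80% upper limit for the placebo rate after no placebo conversions runs from 44% down to 23%. Illustrative power at two-sided 0.20 differs between the extreme splits by about 9 to 39 points. Only the power and threshold figures depend on the assumed level, and only the power figures on assumed conversion rates.

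This is an inconsistency in a core design statement that should be fixed. It does not show that the trial is invalid, and redacted text may already hold the explanation.

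**What to change.** 1. State for Cohort 1 the planned numbers randomised and treated in each arm.
2. Say what 29 counts: enrolled or randomised, with or without replacements and undosed participants, and under one ratio or more.
3. Correct any of the three figures that does not hold, wherever it appears: Protocol summary, Sections 3, 4.1, 5 and 6.1.3, and SAP 1.4. If all three hold, one qualifying sentence is enough.
4. Confirm that the sample size calculation uses the actual split, and restate any power or precision that rests on another.
5. Only if the ratio changed during enrolment, give planned numbers for each ratio period and add an exact analysis stratified by period.

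The cost is rewording and one recalculation. A stated power or precision may become less favourable. The clarification itself adds no participants.
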